4.3.3.4 Sensitivity Analysis IV - Per protocol estimand

The purpose of this sensitivity analysis is to evaluate the primary endpoint with subjects who have no important protocol-deviations which potential impact efficacy assessment (the per protocol set). Subjects with protocol-prohibited medication use are excluded from the PP set. Subjects with at least 2 consecutive, or at least 3 intermittent missing dose for any reason including COVID-19, are also excluded.

This sensitivity analysis will be carried out via a per protocol estimand, which is the same as the composite estimand except with the PP set. A stratified CMH test will be used to estimate the treatment effect; the p-value for the comparison, together with the CMH odds ratio and a 95% confidence interval for the odds ratio will be reported. As with the primary endpoint, the test will be stratified by baseline hemoglobin ($<$ median baseline Hgb vs \geq median baseline Hgb) and geographic region (Japan/Australia, United States, Europe). In the case of completely unbalanced strata (all records within any strata fall within a single treatment arm), the CMH test will be stratified only by baseline hemoglobin.

4.3.4 Subgroup analyses

Definitions of subgroups

The following subgroups will be considered for the selected analyses:

- Age (<65 , ≥ 65)
- Gender (Female, Male)
- Baseline weight (<75 kg, ≥ 75 kg)

- Baseline Hgb level (<median, >= median g/dL)
- Previous rituximab monotherapy use (Yes, No)
- Previous rituximab monotherapy or rituximab and other cytotoxic therapy use (Yes, No)
- Prior thromboembolic events within the last 1 year (Yes, No)
- Previous reculizumab use (Yes, No)

In case of very few subjects (eg, <5) in a category, the cutoff value may be changed to suit the distribution of these factors.

Analysis Methods

The CMH odds ratio and 95% CI will be summarized for the subgroups defined above. As with the primary endpoint, the odds ratios for each subgroup will be stratified by baseline hemoglobin (< median baseline Hgb vs \geq median baseline Hgb) and geographic region (Japan/Australia, United States, Europe). The CMH test may not be stratified in the case of completely unbalanced strata. The consistency of the odds ratio among these sub-populations will be examined by forest plots.

4.4 SECONDARY ENDPOINT(S) ANALYSIS

4.4.1 Key/Confirmatory secondary endpoint(s)

4.4.1.1 Definition of endpoint(s)

Key secondary endpoints are rank ordered by their clinical importance in order to perform a sequential closed testing procedure to protect the type I error. The key secondary endpoints will be tested only when the primary analysis reaches significance. In this case, the key secondary endpoints will be tested using a sequential closed procedure with alpha of 0.05 for each test in the order indicated below:

1. Mean change from baseline in Hgb at the treatment assessment timepoint in BIVV009 arm vs in placebo arm (using Hypothetical estimand)
2. Mean change from baseline in FACIT-F Score at treatment assessment timepoint in BIVV009 arm vs in placebo arm (using Hypothetical estimand)

4.4.1.2 Main analytical approach

1. Mean Change from Baseline in Hgb at the Treatment Assessment Timepoint

The change from baseline in Hgb at the treatment assessment timepoint will be analyzed for the FAS. The primary analysis will be performed according to the Hypothetical Estimand based on the MMRM model, while a sensitivity analysis will be done via De-facto Estimand. Similarly, COVID-specific sensitivity analyses will be performed according to the Modified Hypothetical

Estimand and Modified De-facto Estimand in order to ascertain the results for subjects unaffected by the COVID pandemic. Additional details for these estimands are found below, in [Table 9](#).

Table 9 - Estimands for change from baseline in Hgb

	Hypothetical Estimand	Modified Hypothetical Estimand	De-facto Estimand
Population	FAS	mFAS	FAS
Variable	Change from baseline at treatment assessment time point		
ICE handling	any value after transfusion and prohibited medication is considered missing	any value after transfusion and prohibited medication is considered missing	None
Treatment effect	Difference in mean change from baseline at TAT between BIVV009 and Placebo		

Mixed Model with Repeated Measures (MMRM) will be used for the analysis of such endpoints at study visits (including the treatment assessment time points). The MMRM model will include the baseline value of the endpoint, visit, treatment, and treatment and visit interaction. A heterogeneous Toeplitz (TOEPH) covariance matrix within a subject will be used. For the endpoint at the treatment assessment timepoint (average of Week 23, 25, and 26), the estimate will be calculated as the mean of MMRM estimates at Week 23, 25, and 26 visits.

The pseudo SAS code for MMRM is as follows:

```
Proc mixed data=(ADaM dataset) method=reml;
  class usubjid visit;
  model chg = base visit trt trt*visit/ ddfm = kenwardroger
solution;
  repeated visit / type=TOEPH subject=usubjid;
  estimate 'BIVV009 vs. Placebo at treatment assessment
timepoint' trt 1 -1 trt*visit 0 0 0 0 0 0 0 0 0 0 0 0 0.333
0.333 0.333 0 0 0 0 0 0 0 0 0 0 0 -0.333 -0.333 -0.333
/cl;
run;
```

For either estimand, the mean change from baseline in Hgb at treatment assessment timepoint for both treatment arms, the estimated difference in change from baseline at TAT between BIVV009 and placebo, along with its 95% CI, will be estimated by the MMRM model. The significance test for the treatment difference in Hgb at the treatment assessment timepoint will be based on appropriate treatment contrast.

Additional sensitivity analysis based on multiple imputation will be carried out for the Hypothetical Estimand to evaluate the appropriateness of the assumption of MAR. Specifically, multiple imputation will be performed using a pattern-mixture model and the above MMRM model will be run on the imputed data. Non-monotone missing data will first be transformed to a monotone missing data structure. The control-based imputation method assumes subjects in the

BIVV009 treatment arm who discontinued from the study or are missing Hgb values at the TAT will exhibit similar Hgb values to those subjects in the placebo arm (and subjects in the placebo arm will continue to exhibit those Hgb values). Thus, multiple imputation is performed using only information from the placebo arm.

2. Mean Change from Baseline in FACIT-F Score at Treatment Assessment Timepoint

The derivation of FACIT-F score is detailed in [Section 4.5.1](#). The analyses for hemoglobin described above will be performed for the FACIT-F score and is therefore not repeated here.

Additional sensitivity analysis based on multiple imputation will be carried out for the Hypothetical Estimand to evaluate the appropriateness of the assumption of MAR. Specifically, multiple imputation will be performed using a pattern-mixture model and the above MMRM model will be run on the imputed data. Non-monotone missing data will first be transformed to a monotone missing data structure. The control-based imputation method assumes subjects in the BIVV009 treatment arm who discontinued from the study or are missing FACIT-F values at the TAT will exhibit similar FACIT-F values to those subjects in the placebo arm (and subjects in the placebo arm will continue to exhibit those FACIT-F values). Thus, multiple imputation is performed using only information from the placebo arm.

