### 6.1.3 Weeks 1-25 Part-A

On Days 7, 21, 35, 49, 63, 77, 91, 105, 119, 133, 147, 161, and 175, patients will undergo the following procedures before administration of the study drug:

- Serum or urine pregnancy test in WOCBP (ie, women of child bearing potential), if applicable, on Days 21, 49, 77, 105, 133, and 161
- Physical examination (brief)
- Vital signs
- Hematology panel
- Clinical chemistry panel
- Solicited symptomatic anemia assessment
- QOL assessments:
  - FACIT-Fatigue: all scheduled visits
  - PGIS: Days 35, 77, and 119 only
  - PGIC: Days 35, 77, and 119 only
  - SF-12: Days 35, 77, and 119 only
  - EQ-5D-5L: Days 49, 91, and 133 only
- 12-lead ECG (Day 91 only)
- During Part A, ADA samples will be collected at predose on Day 0, 7, 35, 77, 133, 175 on Day 182 (EOT)
- PK and PD sampling
- Disease-related biomarkers (subset at Day 91 only); refer to the Laboratory Manual for details
- Record healthcare resource utilization data since previous assessment on Days 21, 49, 77, 105, 133, and 161
- Record concomitant medications/procedures including transfusions
- Adverse event monitoring

At 0 hour, study drug will be infused via an indwelling IV catheter over a period of 60 ±5 minutes. Patients with underlying cardiopulmonary disease may receive a 2-hour infusion with Sponsor approval. Additionally, study drug infusion may be interrupted or slowed in the event of suspicion of an allergic reaction or anaphylaxis.

After completion of the infusion, patients will undergo the following procedures:

- Vital signs at 1 hour (±5 minutes) postdose
- 12-lead ECG (Day 91 only) at 1 hour (±15 minutes) postdose
- PK and PD sampling at 1 hour (±15 minutes) postdose

Vaccinations should be administered according to [Section 6.1.1.1](#), if applicable, or [Appendix I](#) for Japan.

Note: Patients who miss a dose (ie, outside the dosing window or >17 days since last dose) should return to the site for an unscheduled visit 1 week prior to the next scheduled dose in order to receive an additional loading dose. The patient should then resume subsequent dosing visits every 14 days after the loading dose.

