5.4 APPENDIX 4 DATA HANDLING CONVENTIONS

Study Day

Study Day is defined as days relative to the date of first dose of study drug (BIVV009 or placebo) in Part A (Day 0 as in the protocol). The Study Day of an event is calculated as

- (date of event – date of first dose of study drug in Part A + 1), if the event is on or after the first dose date;
- (date of event – date of first dose of study drug in Part A), if the event is prior to the first dose date.

The date of the first dose of study drug in Part A is Study Day 1.

Baseline

Baseline measures are defined as the last value prior to the first dose of study drug. If a subject receives a transfusion during the screening period, the baseline measure must be at least 7 days after the transfusion.

Visit Windows

Analysis by study visit will utilize the data recorded on the corresponding nominal visit from electronic Case Report Forms (eCRFs). In case of missing data/assessments for a visit, data from an unscheduled visit, or ET/Safety Follow-up Visit will be used, if the Study Day of such a visit fits in the analytic window defined in [Table 14](#), below. If multiple values are identified within the analytic window, the one closest to the target study day will be used.

[figure not shown]
Table 14 - Analyses window definition

[figure not shown]
Visit	Target Study Day	Analytic Visit Window
Baseline (Day 0)	1	≤1
Week 1 (Day 7)	8	2 – 15
Week 3 (Day 21)	22	16 – 29
Week 5 (Day 35)	36	30 – 43
Week 7 (Day 49)	50	44 – 57
Week 9 (Day 63)	64	58 – 71
Week 11 (Day 77)	78	72 – 85
Week 13 (Day 91)	92	86 – 99
Week 15 (Day 105)	106	100 – 113
Week 17 (Day 119)	120	114 – 127
Week 19 (Day 133)	134	128 – 141
Week 21 (Day 147)	148	142 – 155
Week 23 (Day 161)	162	156 – 169
Week 26 (Day 175)	176	170 – 179
Week 26 (Day 182; EOT Visit in Part A)	183	180 – 189

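### The pseudo SAS contrast for both key secondary endpoints lists 29 coefficients for 28 cells and leaves treatment out of CLASS, so as printed it is not estimable

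*SAP*

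**What the plan says.** Part A SAP 4.4.1.2 states the quantity wanted at the treatment assessment timepoint: "the estimate will be calculated as the mean of MMRM estimates at Week 23, 25, and 26 visits". It then prints a block labelled as pseudo SAS code:

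- The CLASS line is "class usubjid visit".
- The MODEL line is "model chg = base visit trt trt*visit/ ddfm = kenwardroger".
- The ESTIMATE line begins "trt 1 -1 trt*visit 0 0 0 0 0 0 0 0 0 0 0 0 0.333" and continues "0.333 0.333 0 0 0 0 0 0 0 0 0 0 0 -0.333 -0.333 -0.333".

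The text after the block says only that the significance test uses a suitable treatment contrast. The printed line is therefore the only explicit statement of that contrast. The same section carries the Hgb analyses over to the FACIT-F score. SAP 4.4.1.1 and 4.6 place these two endpoints, in that order, in the formal testing sequence after the primary endpoint.

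**The concern.** The words and the code in one section disagree. An average over three visits in each of two arms needs treatment as a two-level factor and one interaction coefficient per arm-by-visit cell. The code has neither: treatment is missing from CLASS, and the coefficient list is one value too long.

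At stake is the pre-specified contrast behind the estimate, confidence interval and test for both key secondary endpoints. It also serves the de-facto and COVID-modified estimands and the control-based imputation analysis, which reruns the same model. If the code were repaired only when it failed at run time, after unblinding, a confirmatory contrast would have been settled with the data in view.

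**Working it through.** **Inputs**

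- Post-baseline dosing visits: Protocol 6.1.3, "On Days 7, 21, 35, 49, 63, 77, 91, 105, 119, 133, 147, 161, and 175, patients will undergo". That is 13 visits, Weeks 1, 3, ..., 25.
- Final Part A visit: Protocol 6.1.4 and SAP Table 14, "Week 26 (Day 182; EOT Visit in Part A". This is the 14th.
- FACIT-F timing: Protocol 6.1.3, "FACIT-Fatigue: all scheduled visits", plus the end-of-treatment visit in 6.1.4. The same 14 visits apply.
- Arms: 2 (SAP 1.1).

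**Step 1: count**

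Cells needed: 2 × 14 = 28.

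Values printed: 12 zeros + three of 0.333 + 11 zeros + three of −0.333 = 15 + 14 = 29.

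The second block is right for 14 visits; the first has one zero too many. Since 29 is odd, it cannot equal two arms times any whole number of visits.

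**Step 2: the code as printed**

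This assumes the usual SAS behaviour: columns follow CLASS order and surplus coefficients are ignored.

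With treatment outside CLASS, treatment has one column and the interaction has 14. The first 14 printed values are 12 zeros, 0.333, 0.333, so the weight falls on Weeks 25 and 26 only. The 14 interaction columns add up to the treatment column, so an estimable contrast must satisfy

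treatment coefficient = sum of interaction coefficients.

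Here 1 ≠ 0.333 + 0.333 = 0.666. The contrast is not estimable. Its largest departure from the estimable space is (1 − 0.666)/15 = 0.022, and a numerical check on a two-arm, 14-visit design matrix gives the same value.

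**Step 3: does adding treatment to CLASS repair it?**

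With treatment in CLASS, the interaction coefficients within each arm must sum to that arm's treatment coefficient (1 and −1). Across the two arms they must sum to zero at each visit, because no visit coefficients are given. Arm 1 is taken as BIVV009.

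| Reading of the 29 values | Where the weights fall | Largest departure |
|---|---|---|
| Treatment before visit | Arm 1: +0.333 at Weeks 25, 26. Arm 2: +0.333 at Week 1, −0.333 at Weeks 25, 26. The 29th value has no cell | 0.148 |
| Treatment after visit | Both arms: +0.333 at Week 13, −0.333 at Week 26. Arm 1: +0.333 at Week 15 | 0.281 |
| Baseline counted as a 15th visit (30 cells) | Arm 1: +0.333 at Weeks 23, 25, 26. Arm 2: −0.333 at Weeks 21, 23, 25 | 0.111 |
| The two rows labelled Week 26 in Table 14 merged (26 cells) | Arm 1: +0.333 at Week 26. Arm 2: +0.333 at Weeks 1, 3 | 0.206 |

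In the first row the arm sums are 0.666 and 0.333 − 0.333 − 0.333 = −0.333, not 1 and −1. No row is estimable, and none gives the Week 23, 25 and 26 difference.

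**Step 4: the corrected vector**

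Put treatment before visit in CLASS and use 28 values: 11 zeros, three of 1/3, 11 zeros, three of −1/3. The arm sums are then 1 and −1, every visit sum is 0, and the departure is about 3 × 10⁻¹⁵, which is zero to machine precision. The contrast is exactly the mean difference over Weeks 23, 25 and 26. With 0.333 in place of 1/3, each block sums to 0.999 and the departure is 0.001/15 ≈ 7 × 10⁻⁵. That is rounding, not a separate defect.

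**The case against.** The strongest reply is that the block is not the specification. It is labelled pseudo code and has a placeholder dataset name. The surrounding text gives the model terms, the covariance structure and the target correctly, and Table 9 agrees with it. A programmer who follows the words would write the right contrast. This largely stands, and it is why the severity is limited. It does not excuse a literal coefficient list that cannot fit the model, given that the text offers no other explicit contrast.

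Two stronger readings are tempting and are not supported.

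- A reader might infer that the code would quietly report an effect at the wrong visits. The misplaced weights in the table arise only if treatment is added to CLASS or the visit count is changed. In every reading tried the result is not estimable, so the realistic outcome is a visible failure, not a biased result.
- A reader might infer that every sensitivity analysis is affected. Those of the primary endpoint (SAP 4.3.3) use the Cochran-Mantel-Haenszel test and do not touch this code.

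It is also conceivable that text extraction from the PDF duplicated a zero. Nothing shows this, and it would not explain the missing treatment factor.

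**Conclusion.** The point holds as an error in the pseudo code, not in the planned estimand or model. The count of 29 against 28 and the absence of treatment from CLASS can both be read off the page. As printed, the contrast weights Weeks 25 and 26 only and is not estimable; both defects must be corrected, because either one alone defeats the contrast.

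Severity is low to moderate. The effect is confined to the repeated-measures analyses of Hgb and FACIT-F. The primary endpoint, its alpha and the sample size are untouched, and the fault would probably surface when the code is run.

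The count rests only on the printed zeros having survived extraction. The placement of weights and the estimability results also assume usual SAS column order and that surplus coefficients are ignored; the documents state neither.

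**What to change.** Before unblinding for the Part A analysis, change two lines of the code in SAP 4.4.1.2:

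- CLASS: `class usubjid trt visit;`
- ESTIMATE: `trt 3 -3`, then `trt*visit` with 11 zeros, `1 1 1`, 11 zeros, `-1 -1 -1`, and the options `divisor=3 cl`.

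State the level order: BIVV009 first for treatment, and Weeks 1 to 26 in time order for visit. Averaging the three visit-level least-squares mean differences would serve equally well and does not depend on a long coefficient list.

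Also correct the Table 14 row in SAP 5.4 that labels Day 175 as Week 26. The Part A dosing schedule puts that day at Week 25, and the duplicate label leaves the visit levels ambiguous.

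The cost is two lines of code, one sentence on level order and one table label. No new data or change to the model is needed.

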4.4.2 Supportive secondary endpoint(s)

Additional analyses for hemoglobin and bilirubin

To further understand the clinical effect of BIVV009 in increasing hemoglobin level compared with placebo, the number of subjects with an increase of hemoglobin level from baseline ≥ 1 g/dL, ≥ 1.5 g/dL, ≥ 2 g/dL and ≥ 3 g/dL at TAT will be reported for BIVV009 and for placebo.

Mean Change from Baseline in Bilirubin by visit (including TAT)

Total bilirubin will be summarized by-visit, including change from baseline, using the Full Analysis Set, with subjects with Gilbert's syndrome or unknown Gilbert's test result excluded.

If the number of subjects with unknown Gilbert's syndrome status is greater than 2, additional sensitivity analysis will be performed to include such subjects (unknown Gilbert's syndrome).

Mean Change from Baseline in Lactate Dehydrogenase (LDH) by visit (including TAT)

LDH will be summarized by-visit, including change from baseline, using the Full Analysis Set.

Additional descriptive analyses will be performed for LDH isoforms.

Incidence of Solicited Symptomatic Anemia

- Incidence of solicited symptomatic anemia will be summarized by visit descriptively using the FAS. The summaries will be based on observed data only and missing grades will not be imputed.

- An improvement in each anemia symptom is defined as at least 1 grade reduction from baseline; whereas worsening is defined as at least 1 grade increase from baseline. The percentage of improved and worsened subjects for each symptom will be presented by visit; this percentage is calculated based on the number of subjects with no missing grade at both baseline and each post-baseline visit.
- The improvement (worsening) in all anemia symptoms is defined as at least 1 grade reduction (increase) in at least 1 symptom, and no worsening (improvement) in other remaining symptoms. The proportion of subjects improved and worsened in all anemia symptoms will be summarized by visit.

4.5 TERTIARY/EXPLORATORY ENDPOINT(S) ANALYSIS

The analysis of exploratory endpoints will be based on the Observed Estimand defined in [Section 1.2.1](#). Additionally, summary of hemolytic parameters (Hgb, bilirubin, LDH, haptoglobin, and reticulocyte) over time (by visit) is included to examine the improvement trend over time. Unless specified otherwise, the endpoints will be summarized by visit for continuous and categorical variables, and for time to event variables (eg, time to obtain Hgb level of ≥ 12 g/dL) for the entire Part A. The analyses for exploratory endpoints will be outlined by the type of endpoints in the following subsection. Details of patient-reported outcomes can be found in [Section 4.5.3](#).

4.5.1 Definition of endpoint(s)

Continuous Endpoints

The continuous endpoints include:

- Mean change from baseline in QOL, as assessed by the change in the five level EQ-5D-5L scores at the treatment assessment timepoint (TAT) and by visit
- Mean change from baseline in QOL, as assessed by the change in the 12-item short form survey (SF-12®) at the end of treatment assessment endpoint and by visit
- Mean change from baseline in hemolytic parameters (Hgb, total bilirubin, LDH, haptoglobin, and absolute reticulocyte) by visit
- Mean change from baseline in FACIT-F by visit

Response (Categorical) Endpoints

The response endpoints include (order different from protocol and not reflecting importance):

- Incidence of thromboembolic events after the first 5 weeks of study drug administration
- Incidence of CAD-related symptoms at last scheduled visit of Part A
- Total healthcare resource utilization at EOT (Part A)
- Proportion of subjects normalizing Hgb (≥ 12 g/dL) at TAT and by visit
- Proportion of subjects achieving 1.5 g/dL increase in Hgb at TAT and by visit
- Proportion of subjects normalizing bilirubin at TAT and by visit

- Proportion of subjects normalizing LDH at TAT and by visit (Proportion of subjects with $LDH \leq 1.5 \times ULN$ at TAT will also be reported)
- Proportion of subjects normalizing haptoglobin at TAT and by visit
- PGIC and change from baseline in PGIS to assess subject's perception of changes in CAgD disease burden at last scheduled visit of Part A

Time-to-Event Endpoints

Time-to-event endpoints include:

- Time to first transfusion after the first 5 weeks of study drug administration from the first dose of study drug
- Time to first transfusion (including the first 5 weeks of study drug administration) from the first dose of study drug
- For subjects who do not receive any transfusion, their time-to-event will be censored at the study day of the last scheduled visit in Part A.
- Time to first normalization of bilirubin from the first dose of study drug
- Time to first normalization of LDH from the first dose of study drug
- Time to first normalization of haptoglobin from the first dose of study drug
- Time to first normalization of Hgb level (≥ 12 g/dL)
- Time to first achieving 1.5 g/dL increase in Hgb level

